7.5.4.9 Concomitant Medications

Concomitant medications will be reviewed and recorded at each study visit. A discussion of concomitant medications is provided in Section [7.4.4](#).

7.5.4.10 Pregnancy Testing

Female subjects of childbearing potential will have urine pregnancy tests as specified in the Schedule of Events ([Table 2.1](#) and [Table 2.2](#)). Female patients with a positive pregnancy test at Baseline do not meet eligibility criteria for enrollment and will not be enrolled in the study. Females considered not of childbearing potential include those who have had total hysterectomy, have been in menopause for at least two years, or have had tubal ligation at least one year prior to Baseline.

Additional pregnancy tests will be performed at any visit in which pregnancy status is in question. A serum pregnancy test will be performed in the event of a positive or equivocal urine pregnancy test result.

Experience with UX001 in pregnant women is limited. The study drug may involve risks to a pregnant female or unborn baby which are currently unknown. Participants of child-bearing potential or with partners of child bearing potential who have not undergone a bilateral salpingo-oophorectomy and are sexually active must consent to use a highly effective method of contraception as determined by the site investigator from the period following the signing of the informed consent through 30 days after last dose of study drug. Examples of highly effective methods of contraception include oral hormonal contraceptives, patch hormonal contraceptives, vaginal ring, intrauterine device, physical double-barrier methods, surgical hysterectomy, vasectomy, tubal ligation or true abstinence (when this is in line with the preferred and usual lifestyle of the subject), which means not having sex for the duration specified above because the subject chooses not to.

7.5.4.11 Pregnancy in Subject or Partner

Pregnancies in subjects or partners must be reported within 24 hours of knowledge of the event to Ultragenyx or its designee. The investigator must make every effort to follow the pregnancy of either subject or partner through resolution of the pregnancy (delivery or termination) and report the resolution to Ultragenyx or its designee. In the event of a pregnancy in the partner of a subject, the investigator should make every effort to obtain the

female partner's consent for release of protected health information. Refer to the Study Reference Manual for details on the reporting procedures to follow in the event of pregnancy.

7.5.5 Drug Concentration Measurements

Blood samples for the measurement of trough levels of free serum SA will be drawn at the time points shown in the Schedule of Events ([Table 2.1](#) and [Table 2.2](#)); samples will be obtained from the subjects during blood draws for clinical laboratory samples.

Urine samples for measurement of free serum SA will be collected during Part I of the study only. The time elapsed from the last dose of study drug should be noted. SA, the active study drug in UX001-CL202, occurs naturally in the human body, both through de novo synthesis and via the diet. Consequently, the free serum SA level should reflect, but will not be a quantitative measure, of circulating study drug. Refer to the central laboratory manual for details on the drug concentration measurements.

7.5.6 Appropriateness of Measures

The efficacy parameters to be evaluated in this study include clinical changes in muscle strength, and subject mobility, and function. The clinical assessments in the study employ standard performance measures used in other neuromuscular diseases and conditions that cause muscle weakness and impaired function. Based on the work of Aitkens ([Aitkens et al. 1989](#)), the study will focus on quantitative muscle testing. The strength of a set of muscle groups in the upper and lower extremities will be assessed by HHD, a form of quantitative muscle testing that uses a device with a strain gauge to measure force during a MVIC ([Sisto et al. 2007](#)). Walking ability will be assessed using the 6MWT test, a commonly used test of endurance used in clinical trials for various indications that has served as the basis for many product approvals. In addition, an interview-based measure designed to evaluate disability in GNE Myopathy patients (HIBM-FAS) will be administered in this study to further validate the instrument.

Exploratory measures will attempt to identify changes in serum biomarkers in Part I of the study. Serum NCAM may be evaluated to provide some estimate of the sialylation of NCAM in the regenerating muscle, albeit at low levels in the circulation. Other biomarkers of muscle injury (e.g., MMP9 and microRNAs) may also be assessed. However, interim data from the UX001-CL201 study suggests the results may be of limited value; therefore, exploratory serum protein markers will not be assessed in Parts II, III, and IV of the study.

Serum CK level will be assessed as a measure of muscle injury throughout the study; a positive dose-dependent decrease in serum CK levels was observed in the UX001-CL201 Week 24 analysis. Unlike other myopathies, CK activities are mildly elevated or in the normal range for these patients; 22/58 patients reported by three publications had two-times or higher elevations ([Sadeh et al. 1993](#)); ([Mizusawa et al. 1987](#)); ([Sunohara et al. 1989](#)). The mouse model of HIBM showed elevated CK levels that improved substantially on treatment ([Malicdan et al. 2009](#)). Given the modest CK levels in patients, it is unclear if this

is a universally evaluable endpoint in humans, however in the mouse model, the data on reduced CK levels during SA treatment was compelling ([Malicdan et al. 2009](#)).

The safety parameters to be evaluated in this study include standard assessments such as recording of medical history, AEs and SAEs, physical examination, neurological examination, vital signs, serum chemistry, and other routine clinical and laboratory procedures. In addition, symptoms of increasing muscle weakness and pain which are characteristic of myopathy will be recorded.

7.6 Statistical Methods and Determination of Sample Size

Because the completeness of the data affects the integrity and accuracy of the final study analysis, every effort will be made to ensure complete, accurate and timely data collection, and to avoid missing data. In particular the endurance measures will be performed in duplicate using standard and consistent methodology. The detailed method for analyses will be presented in the Statistical Analysis Plan (SAP); the information below is intended as a guide to planned analyses.

7.6.1 Clinical and Exploratory Efficacy Measures

The clinical evaluation measures in this study are:

- Improvement in quantitative muscle strength as measured by HHD.
- Improvement in mobility, strength and gross motor function as measured by the 6MWT and walking speed and weighted arm lift tests.
- Improvement in functional disability as measured by the HIBM-FAS.

The exploratory efficacy measures in this study will involve evaluation of novel biomarkers of sialylation and muscle injury. The exploratory efficacy measures may include:

- Improvement in serum biomarkers of muscle injury, including CK.
- Improvement in other serum biomarkers of muscle injury, sialylation, and remodeling, including MMP9 (metalloproteinase level) and specific microRNAs associated with muscle disease.

Serum biomarkers of sialylation will be evaluated as exploratory analyses in Part I of the study only. Serum CK levels will be evaluated in Parts I, II, III, and IV of the study.

7.6.1.1 Clinical Efficacy Analyses

All subjects with any post-dose data will be included in the intent-to-treat (ITT) efficacy analysis.

Efficacy will be evaluated by continued improvement in clinical assessments. Efficacy assessments may differ depending on the phase of the study (i.e., Part I, Part II, Part III, or

Part IV). For Part I efficacy evaluation, results from the last pre-treatment assessment from UX001-CL201 will be compared with the last post-treatment assessment for the Part I Treatment Period as listed in the Schedule of Events ([Table 2.1](#)), with efficacy conclusions based on change since SA-ER treatment initiation. An interim analysis will be conducted when a majority of subjects have completed the Month 6 Visit of the Part II Treatment Period. For Part II efficacy evaluation of the continuing subjects, change from baseline of Part II to Month 6 assessment at 12g/day SA-ER/SA-IR dose will be determined and compared with the improvement observed during the first 6 months of treatment with 6 g/day SA-ER dose, and to the rate of change observed with placebo or 3g treatment during the first 6 months of the study.

The changes from baseline of the treatment-naïve subjects will be evaluated over time. Potential comparisons of the changes from baseline to Month 6 will be performed for the 6MWT, UE, and LE between the naïve group versus the placebo and 6g/day treatment groups for the first 24 weeks of treatments in subjects able to walk more than 200m at baseline. In addition, changes in muscle strength over the entire treatment period of subjects who started with 6g/day and 3g/day will be evaluated and compared to the projected values of subjects who received placebo for the first 24 weeks of treatment in UX001-CL201.

A full accounting of the analyses for Parts III and IV of the study will be provided in the Statistical Analysis Plan.

For those clinical evaluations with repeated assessments (i.e., HHD, 6 MWT, walking speed and weighted arm lift tests) the analysis will be performed using a repeated measures analysis. An exchangeable variance-covariance structure will be used. The final treatment effect estimate based on this model will be the estimated treatment difference at Month 36. The purpose of including data from assessments prior to Month 36 is to increase the precision of the estimated variance, while using categorical effects of time-by-treatment to avoid modeling assumptions.

Muscle strength as measured by HHD will be reported as force in kg and percent of predicted normal force based on age, gender, height and weight (where applicable). Changes in force and percent of predicted normal force will be assessed for gross grip, pinch, shoulder abductors, elbow flexors, elbow extensors, hip abductors, hip adductors, hip flexors, hip extensors, knee flexors, and knee extensors. Individual muscle groups will also be compared to assess individual muscle changes.

Walking ability as measured by the 6MWT will be reported as distance in meters and percent of predicted normal based on age and gender. Changes in distance and percent of predicted normal will be assessed. The proportion of subjects with a normal percent predicted distance walked (i.e., a percent predicted distance walked of $\geq 80\%$) at each time point may be tabulated. The relationship between 6MWT results and other and efficacy outcomes may also be explored.

Walking speed as measured by the 25 feet walk test will be reported in seconds and percent of predicted normal for each walking speed. Changes in the number of seconds and percent of predicted normal for each speed from Baseline will be assessed.

Arm raising ability as measured by the weighted arm lift test will be reported as the total number of completed repetitions. Changes from Baseline in repetitions between the treatment arms will be assessed.

Functional disability as measured by the HIBM-FAS will be reported as a total score and subscale scores for mobility, self-care, and upper extremity function, with lower scores associated with greater disability. Changes in the total score will be assessed.

7.6.2 Safety Measures

The safety measures in this study are:

- Incidence and frequency of AEs and SAEs
- Clinically significant changes from baseline in vital signs, physical and neurological examination findings and laboratory evaluations
- Interval history, including reported symptoms of increasing muscle weakness or pain, and incidence of falls

The analyses of safety will include all subjects who receive any study drug at any time during the study and provide any post-treatment safety information. Safety data will be periodically reviewed by the DMC.

For the safety analysis, the incidence and frequency of AEs and SAEs will be evaluated. All AEs will be coded using the Medical Dictionary for Regulatory Activities (MedDRA). The incidence and frequency of AEs will be summarized by System Organ Class (SOC), Preferred Term (PT), relationship to study drug, and severity for each treatment group. A by-subject listing will be provided for those subjects who experience a SAE, including death, or experience an AE associated with early withdrawal from the study or study drug.

Clinical laboratory data will be summarized by the type of laboratory test. The frequency and percentage of subjects who experience abnormal clinical laboratory results (i.e., outside of reference ranges) and/or clinically significant abnormalities after study drug administration will be presented for each clinical laboratory measurement. For each clinical laboratory measurement, descriptive statistics will be provided for Baseline and all subsequent post-treatment scheduled visits. Changes from Baseline to the post-treatment visits will also be provided. Descriptive statistics of vital signs, imaging assessments, and concomitant medications will also be provided in a similar manner.

The SAP will provide additional details on the planned statistical analysis.

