6.5 General Considerations for Statistical Analysis

All statistical tests will be two-sided and a difference resulting in a p-value of less than or equal to 0.05 will be considered statistically significant. All p-values will be rounded to and displayed in four decimals. If a p-value less than 0.0001 occurs it will be shown in tables as <0.0001.

There will be no multiplicity adjustments, or adjustments for multiple comparisons.

Descriptive summaries of variables will be provided where appropriate. For continuous variables, the number of non-missing values (n) and the median, mean, standard deviation, minimum, and maximum will be tabulated by treatment. For categorical variables, the counts and proportions of each value will be tabulated by treatment. Expansion of descriptive table categories within each treatment may occur if such elaborations are thought to be useful.

All collected data will be presented in listings. Data not subject to analysis according to this plan will not appear in any tables or graphs but will be included in the data listings.

Post-hoc exploratory analyses not identified in this SAP may be performed to further examine the study data. These analyses will be clearly identified as such in the final clinical study report. The SAP will not be amended for post-hoc, additional analyses identified after planned analyses are completed. Likewise, the list of planned tables (Section 8.1) is the list of planned tables prospectively defined for the study analyses. Additional tables and figures may be defined to further evaluate study results and the SAP will not be amended to list these additional analysis tables.

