6.5.4 Data Handling

Unscheduled or repeated laboratory results will not be analyzed for the summary of continuous values but may be included in any post-hoc laboratory shift tables as follows. Unscheduled tests will be included with the time of the nearest regularly scheduled test. If there is a scheduled laboratory result and one or more unscheduled tests assigned to the same time point, the most conservative test (i.e., a test with low or high results) will be used. Repeated tests will be included only if they reflect abnormal (low or high) results and the corresponding original results are normal.

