6.10 Statistical Analysis: Safety

In general all safety analyses will be completed using descriptive summaries, graphs, and subject listings. No planned inferential testing of safety endpoints is planned. If after the any planned analysis it is determined by the medical writer and study medical monitor that inferential tests of significance may help to provide context for safety information these tests may be performed and identified in the CSR.

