6.10.2 Clinical Laboratory Parameters

Clinical safety laboratories (CBC, Chemistries, Creatine Kinase, Free Serum SA Levels, and Pregnancy tests) will be assessed during Part I of this study at baseline and the Part I termination visit. For subjects who roll-over from study UX001-CL201 the baseline clinical laboratory values may be derived from the last visit (week 48, or termination visit) in UX001-CL201, prior to participation in UX001-CL202.

Clinical safety laboratories (CBC, Chemistries, Creatine Kinase, and Free Serum SA Levels) will be assessed during Part II of this study at the Screening/Baseline and Months 1, 3, 6, 12, 18, 24, 30, 36, and termination visits. Pregnancy testing will be completed in Part II at the Screening/Baseline and Months 12, 24, and termination visits. For subjects who roll-over

from study UX001-CL201 and participate in Part I of this study the baseline clinical laboratory values may be derived from the last visit in Part I (Part I termination visit). For Treatment Naïve Subjects enrolled directly into Part II the baseline values will be the Screening/Baseline visit for these subjects.

Laboratory data will be monitored for safety and will be listed by subject. No descriptive information will be compiled for clinical laboratory data.

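### The laboratory count in Protocol 7.6.2 has no baseline condition or common window, and no planned laboratory table separates new abnormalities from pre-existing ones

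*Protocol*

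**What the plan says.** Protocol 7.6.2 commits to reporting, for each laboratory measurement, the percentage of "subjects who experience abnormal clinical laboratory results (i.e., outside of reference ranges) and/or clinically significant abnormalities after study drug administration". The sentence names no baseline status, visit or time window, so its natural reading is an ever-abnormal count. The same section lists the safety measure as "Clinically significant changes from baseline in vital signs, physical and neurological examination findings and laboratory evaluations". Directly after the count it plans descriptive statistics by visit and adds: "Changes from Baseline to the post-treatment visits will also be provided".

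The SAP takes a different line. Section 6.10.2 provides subject listings and states: "No descriptive information will be compiled for clinical laboratory data". The table list in SAP 8.1 has no safety-laboratory abnormality table and no shift table. The only mention of shift tables is in SAP 6.5.4, where unscheduled and repeat results "may be included in any post-hoc laboratory shift tables as follows". SAP 6.5.1 nevertheless describes its analyses as consistent with the protocol.

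**The concern.** The count does not measure what the section says it will measure. A safety measure defined by change from baseline is reported through a percentage that ignores baseline. In a muscle disease this matters most for CK, which is on the chemistry panel (Protocol Table 7.5.4.7.1). A subject whose CK is high at entry and then stays flat, or falls, is still counted as abnormal after study drug.

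The second problem is opportunity. An ever-abnormal percentage rises with the number of samples, and the Parts of this study are sampled unequally. There is no concurrent control, so each subject's own baseline is the main safeguard against misreading. Adverse events have such a rule in SAP 6.5.3 (onset or worsening after first dose). Laboratory results have none.

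At stake is how a descriptive safety table would be read: a high background could hide a real change, and a sampling difference could look like a dose difference.

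**Working it through.** The documents give no laboratory incidence to reproduce. The checks below use the visit schedule and stated assumptions.

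**1. Pre-existing CK elevation.** Protocol 7.5.6 reports that "22/58 patients reported by three publications had two-times or higher elevations": 22/58 = 37.9%. Two-fold elevation is a stricter criterion than out of range, so in those publications the out-of-range share was no smaller. If this cohort resembled them (an assumption), about 46 × 0.379 = 17.4 roll-over subjects would be flagged without any change in CK.

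**2. Scheduled post-baseline samples** (Protocol Tables 2.1 and 2.2; SAP Tables 1 and 2; SAP 6.7.13).
- Part I, 6 g/day: the Part I Termination Visit only, so 1.
- Part II to Month 6, 12 g/day: Months 1, 3 and 6, so 3.
- Parts II to IV in full: Months 1, 3, 6, 12, 24 and 36, plus Termination, so 7.

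**3. Chance of at least one out-of-range result with no drug effect.** Assume that the reference range covers 95% of values per test. With independent samples the chance is 1 − 0.95^k, so k = 3 gives 1 − 0.857 = 14.3%. For correlated samples, normal values with a shared subject component were simulated (1,000,000 subjects).

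| Samples | Correlation 0 | 0.5 | 0.8 |
|---|---|---|---|
| 1 (Part I) | 5.0% | 5.0% | 5.0% |
| 3 (Part II to Month 6) | 14.3% | 12.5% | 9.8% |
| Ratio | 2.9 | 2.5 | 2.0 |

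For 46 subjects with independent samples, this is 2.3 against 6.6 flagged per analyte.

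**4. Would a baseline condition alone be enough?** At correlation 0.8, 44% of subjects flagged on one sample, and 35% of those flagged on three, were already out of range at baseline. The condition therefore removes a real share. Among subjects in range at baseline, however, the figures are still 2.9% against 6.7% (ratio 2.3) at correlation 0.8, and 4.3% against 11.1% (ratio 2.6) at correlation 0.5. The sample-count effect remains unless results are shown visit by visit or over equal windows.

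**5. The whole study.** Part III reduces the dose to 6 g/day for subjects without added benefit (Protocol 7.1). Counting Termination with the last dose, a roll-over subject stepped down after Month 6 has 3 samples at 12 g/day and 1 + 4 = 5 at 6 g/day. After Month 12 the split is 4 and 1 + 3 = 4. Totals for 46 + 10 subjects, with no dropout and 0 to 15 roll-overs assumed to stay on 12 g/day:
- Step-down after Month 6: 208 to 268 samples at 12 g/day, against 230 to 170 at 6 g/day.
- Step-down after Month 12: 254 to 299, against 184 to 139.

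The direction of the imbalance therefore depends on when subjects step down and how many do.

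**The case against.** The strongest reply is that baseline is not ignored. Protocol 7.6.2 plans baseline values, by-visit statistics and changes from baseline in the same paragraph. CK has its own baseline-adjusted model (SAP 6.7.13) and planned tables. New or worsening laboratory findings reported as adverse events appear in the TEAE tables by dose (SAP 6.5.3 and 6.10.1). This stands, and it rules out any claim that the plan disregards baseline altogether. It does not rescue the count: group changes and a mean CK model do not show which flagged subjects were normal beforehand, and the TEAE route depends on the investigator reporting the result.

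A reader might also infer that the plan sets up a false dose effect. The text does not go that far. In 7.6.2 the phrase about treatment groups belongs to adverse events, not to the laboratory count, and the SAP says of safety endpoints: "No planned inferential testing of safety endpoints is planned". Under SAP 6.10.2 the table would not be produced at all. A display by dose is nonetheless plausible. SAP 5.1 focuses safety on the 6 g/day and 12 g/day doses, SAP 5.3 summarizes safety variables by Part, and SAP 6.5 says: "For categorical variables, the counts and proportions of each value will be tabulated by treatment". If the table the protocol promises is restored, this counting rule is the one on the page.

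Finally, a reader might compare 7 samples with 1 and quote 30.2/5.0, about 6-fold. That assumes every sample after Part I was taken at 12 g/day. It fails for every subject stepped down in Part III. The seventh sample is also taken four weeks after the last dose and is not required of subjects entering UX001-CL302.

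**Conclusion.** The point holds in a limited form. As written, the count mixes pre-existing with new abnormalities and has no common window, and no planned laboratory table corrects for either. If it is shown by Part or dose, Part II to Month 6 would exceed Part I about 2- to 3-fold per analyte with no drug effect. That size rests on a 95% reference range and within-subject correlation of 0 to 0.8, neither of which the documents give. No multiple should be quoted for the full study, because the imbalance varies and can reverse.

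The CK figure is a literature rate, not a measured rate in this cohort. Misreading as a drug effect is a risk of interpretation, not a planned result. This is an inexpensive improvement to a descriptive safety summary in a study that is not powered for comparisons.

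**What to change.** In Protocol 7.6.2 and SAP 6.10.2, replace the ever-abnormal count with treatment-emergent abnormalities: in range (or a lower grade) at baseline, then out of range (or a higher grade). Present them as baseline-to-visit shift tables at each scheduled visit, by the dose being taken when the sample was drawn. Put Termination in its own row, since it is off drug.

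State the laboratory baseline first. SAP 5.3 uses the last UX001-CL201 value for roll-over subjects, while SAP 6.10.2 allows the Part I Termination value; both were taken on drug. Reconcile them as follows:
- For the move to 12 g/day: the Part I Termination value. For roll-over subjects who went straight to Part II (SAP Figure 1 note), use the last value before the first 12 g/day dose.
- For roll-over subjects, in addition: the last value before first SA exposure in UX001-CL201, so that abnormalities arising on earlier SA dosing are not classed as pre-existing. SAP 6.5.8 already uses Week 0 or Week 24 in this way for efficacy.
- For treatment-naïve subjects: the Screening/Baseline value.

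While editing, align the SAP 6.10.2 text, which lists laboratory visits at Months 18 and 30, with SAP Table 2, which does not.

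The cost is a modest amount of extra table programming and bringing in the UX001-CL201 laboratory data. No new assessments are needed.
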